10.8.2 Overall Survival

The definition of OS is the time from randomisation to death due to any cause. This is calculated as:

OS(days) = (Date of (Death or Censoring) - Date of Randomization) + 1

The OS for patients without a reported date of death at the time of data cut off or end of study, will be censored at the date last known to be alive.

10.9 Disease Response

10.9.1 Overall Visit Response

The first on study imaging assessment should be performed at Visit 5 (Week 9 ± 1 week), and then every 6 weeks (± 1 week) through the first year, and every 9 weeks (± 1 week) thereafter for up to 24 months. Tumour assessments will be conducted from the date of randomisation and continue until PD, irrespective of treatment discontinuation.

RECIST v1.1 will be used to determine each patient's overall visit response according to target lesions, non-target lesions (NTLs) and new lesions (Table 3). The overall visit responses are recorded on the Disease Response page of the eCRF, however these will be programmatically re-derived based on the target response, non-target response, and new lesion indicator, also collected on the Disease Response page of the eCRF for each visit. The derived overall visit response will be used in the analysis of secondary endpoints.

TLs	NTLs	New Lesions	Overall Visit Response
CR	CR	No	CR
CR	Non-CR / Non-PD	No	PR
CR	NE	No	PR
PR	Non-PD / NE	No	PR
SD	Non-PD / NE	No	SD
NE	Non-PD	No	NE
PD	Any	Yes / No	PD
Any	PD	Yes / No	PD
Any	Any	Yes	PD

Table 3.Overall Visit Response

10.9.2 Best Objective Response

The BOR is selected as the best response of the individual programmatically derived overall visit responses, in sequential order from are CR, PR, SD*, PD and not evaluable (NE),

* Note that for SD, the patient must be stable at or after the first scheduled scan at 9 weeks (+/- 1 week). If an unscheduled scan is conducted prior to the week 9 assessment and shows SD, it will be listed but not included in the summary of BOR.

In cases where an overall visit spans multiple days, determination of the date on which the BOR occurred will follow these rules;

- For SD, the earliest of the dates contributing towards the overall visit assessment will be used.
- For CR or PR, the latest of the dates contributing towards the overall visit assessment will be used.

In order to account for intercurrent events;

- Only values prior to the occurrence of premature study discontinuation or the use of alternative or additional therapy including a new anti-cancer therapy will be considered.
- Where a patient prematurely discontinues treatment, all values will be considered up to the point of PD.

In cases where a patient has no evaluable post-baseline assessments, but presents evidence of either death or PD, the BOR will be imputed as PD.

10.9.3 Objective Response Rate

The ORR (as per RECIST v1.1) is defined as the number (%) of patients with a BOR of CR or PR. The denominator will be based on the FAS, limited to those who have measurable disease at baseline. Patients who discontinue

treatment without PD and go on to have a CR or PR after receiving subsequent systemic anti-cancer therapy will not be considered a responder.

10.9.4 Duration of Response

The DoR is defined as the number of days from the date of first documented CR or PR until the date of first documented PD or death in the absence of PD, whichever is earlier. The number of patients in the FAS with measurable disease at baseline and had a best overall response of CR or PR, will be used.

DoR(days) = (Earliest Date of PD or Death - Earliest Date of CR or PR) + 1

If a patient does not experience PD following an initial CR or PR, then the corresponding DoR will be censored using the same rules defined for PFS (See Section 10.8.1).

10.9.5 Disease Control Rate

The DCR is the number (%) of patients achieving a BOR of CR, PR or SD. The denominator for DCR related analyses will be the same as described for ORR (See Section 10.9.3).

10.10 Adverse Events

10.10.1 Treatment-Emergent Adverse Events

A treatment-emergent adverse event (TEAE) is an AE that occurs, having been absent before the first dose of IMP, or having worsened in severity or seriousness after the first dose of IMP, up to and including 28 days after the date and time of last dose of IMP.

Any AEs that occur 28 days after the date of the last dose of IMP will be considered a post-treatment AE and will be listed only.

10.10.2 AEs Leading to Discontinuation of Study

AEs leading to discontinuation of the study will be identified from the *question "Did the adverse event cause the patient to be discontinued from the study?"* on the Adverse Events eCRF page.

10.10.3 TEAEs Leading to IMP Withdrawal

A TEAE will be classified as an TEAE leading to study drug withdrawal if the answer to the question *"Action Taken with IMP (Setanaxib/Placebo)"* on the Adverse Events eCRF page is "Drug Withdrawn" or "Unknown".

Instances of "Adverse Event" recorded as a reason for discontinuation of IMP on the End of Treatment (IMP) eCRF page will also be considered TEAEs leading to study drug withdrawal. Taking a conservative approach, patients from both sources will contribute to summaries of TEAEs leading to IMP withdrawal, although only counted once if they appear in both.

10.10.4 IMP-Related TEAEs

A TEAE will be classified as related to study drug if the *"Relationship to IMP (Setanaxib/Placebo)"* is assessed as "Related". Any AEs with a missing relationship, will be conservatively categorised as "Related".

10.10.5 AESIs

AESIs will be programmatically identified using the MedDRA codes provided in Section 15.2.

10.11 Electrocardiogram Parameters

All 12-lead ECG results will be recorded within the eCRF, the exception being the RR interval which will be derived using the formula given;

$$RR (msec) = \left(\frac{60,000}{Heart Rate (bpm)}\right)$$

QTcF values will be categorised using the following intervals as specified in the International Council for Harmonisation (ICH) Topic E14;

Absolute Values

•

• ≤ 450 msec

- Change from Baseline
- > 450 msec to ≤ 480 msec > 480 msec to \leq 500 mssec
- ≤ 30 msec > 30 msec to \leq 60 msec
- > 60 msec

> 500 msec

10.12 Eastern Cooperative Oncology Group (ECOG) Performance Status

ECOG	ECOG Performance Status
0	Fully active, able to carry on all pre-disease performance without restrictions
1	Restricted in physically strenuous activity but ambulatory and able to carry out work of a light or sedentary nature, e.g., light house work, office work
2	Ambulatory and capable of all self-care but unable to carry out any work activities; up and about more than 50% of walking hours
3	Capable of only limited self-care; confined to bed or chair more than 50% of walking hour
4	Completely disabled; cannot carry on any self-care; totally confined to bed or chair
5	Dead

10.13 Handling of Missing Dates

Imputation for partial dates prior to enrolment (e.g. date of initial diagnosis) will be performed only if the month and year are known, using the earliest possible date (e.g. 1st of the month). For the purposes of assigning AEs as TEAEs or medications as prior/concomitant, imputation of partial dates will be performed. The imputation rules for AEs and medications are outlined in Appendix 15.1.

Listings will display the collected date and not the imputed date.

11.0 Interim Analyses

11.1 IDMC Reviews of Safety and Tolerability

Safety and tolerability data will be regularly reviewed by an unblinded IDMC, with the first assessment after approximately 12 patients (6 per treatment group) have had the opportunity to complete at least one cycle of pembrolizumab +/- setanaxib, followed by periodic assessments at a frequency defined in the IDMC Charter. The role and responsibilities of the IDMC will be outlined in the IDMC Charter, whilst the TLFs for the IDMC meetings are documented in the IDMC SAP.

11.2 Sponsor Review of Gene Expression and Biomarker Data

The Sponsor will conduct an interim review of initial gene expression and biomarker data in tumour tissue. This will occur after approximately 12 patients (6 per treatment group) have completed their Baseline and post-treatment biopsy. The review will be performed by personnel who are not part of the main study team. For further details, please refer to the standalone Biomarker Analysis Plan.

12.0 Statistical Methods

With the exception of the unblinded statistician and programmers supporting the IDMC, all personnel involved with the analysis of the study will remain blinded until the initial database soft lock at the time of the primary analysis. Further details on the blinding and unblinding are given in the study Blinding Plan.

In this study, it is planned to recruit approximately 35 investigational centres in USA and Europe. Unless specified otherwise, data from all participating sites will be combined for the analysis, so that an adequate number of patients will be available for analysis. In the event that a single site enrols a large proportion of patients, a site effect may be explored as described in Section 12.5.5, otherwise no site effect will be assessed.

All table summaries will be presented by treatment group (including an overall group for safety tables) and by analysis visit where appropriate. Unscheduled visits will be windowed as described in Section 10.4. Unscheduled visit values will contribute to any assessment of worst/most severe results, but otherwise will only be displayed in listings. Additional details related to specific presentations are given in programming notes of the supporting TFL shells.

Categorical variables will be summarised descriptively using counts and percentages. Percentages will be rounded to one decimal place, except 100%, which will be displayed without any decimal places and percentages will not be displayed for zero counts.

Continuous variables will be summarised using univariate statistics, including the number of observations (n), mean, standard deviation, median, minimum and maximum. The minimum and maximum values will be displayed to the same level of precision as the raw data, the mean and median to a further decimal place and the standard deviation to two additional decimal places. In addition, for tumour and biomarker summaries, the geometric mean and the interval of (geometric mean +/- geometric standard deviation) may also be presented.

Analyses will be performed using SAS® (SAS Institute, Cary, NC, US) version 9.4 or higher.

12.1 Patient Disposition

The disposition of patients in the All Enrolled Analysis Set will be summarised descriptively for;

- Non-Randomised Patients, along with the reasons for non-randomisation.
- Patients within each analysis set.

Additionally, patients in the All Randomised Analysis Set who are still on-treatment, who completed/discontinued treatment and who completed/discontinued study, along with the reasons for completion/discontinuation will also be summarised.

Patients in the Full Analysis Set will also be summarised descriptively by geographical region (North America, Europe) and country.

All enrolled patients will be presented in a listing along with indication of study completion, date of completion/discontinuation, primary reason for discontinuation and date of first study dose and last study dose. An additional listing will be provided for patients who are not randomised and the associated reasons.

12.2 Demographic and Baseline Characteristics

The demographics, baseline characteristics and medical history (including SCCHN cancer history) will be presented for patients in the Full Analysis Set.

The demographic and baseline variables, including age (years), height (cm), weight (kg), body mass index (BMI) (kg/m²), ECOG performance and HPV status will be summarised descriptively. The categorical variables for sex (including childbearing potential for females), ethnicity and race will be presented by frequency and percentage.

The disease characteristics of patients' SCCHN cancer history will be summarised descriptively for lymph nodes, lymph node location, laterality and directionality and the tumour, node, metastasis (TNM) stage of disease at diagnosis. The time since diagnosis will also be presented.

Medical history will be coded using the Medical Dictionary for Regulatory Activities (MedDRA), version 25.0 or higher, and summarised by system organ class (SOC) and preferred term (PT).

Listings will be presented for demographic and baseline characteristics, medical history and SCCHN cancer history separately.

12.3 Treatments

12.3.1 Extent of Study Drug Exposure

Exposure will be summarised for patients in the Safety Analysis Set. Descriptive statistics will be provided for both treatment components for the duration of exposure (weeks), the number of doses/infusions administered and cumulative dose received (mg).

The following summaries will be provided for IMP only. Actual and relative dose intensities as well as overall treatment compliance. The number and percentage of patients with overall compliance $\geq 80\% - \leq 120\%$ will be presented. Patients with at least one dose reduction, at least one missed dose along with the recorded reasons for reduced or missed doses will also be presented.

Dose administration, drug accountability and overall treatment compliance will also be listed.

12.3.2 Prior and Concomitant Medications

All medications received will be coded using WHO Drug Dictionary (WHODD) (Version March 2022 [Global B3] or higher).

Both prior and concomitant medications will be summarised separately for patients in the Safety Analysis Set and will be presented by preferred drug name.

A listing will be presented for all, including post-treatment, medications along with indication as to whether each record was prior, concomitant or post treatment.

A summary of the number of therapies for prior systemic anti-cancer therapy regimens, prior radiation therapies, prior/on-study cancer surgeries, subsequent systemic anti-cancer therapy regimens and subsequent radiation therapies will be presented. All of these therapies will also be listed.

12.4 Protocol Deviations

Important protocol deviations are defined in the Protocol Deviation Guidance Document for the study and will be entered into the system of record (PSO). The study team and the Sponsor will conduct on-going reviews of the deviation data from PSO to identify the important deviations impacting the primary efficacy endpoints on a case by case basis. Site level deviations will be applied to all patients actively participating in the study at the time of the site level deviation. Final review of protocol deviations will be conducted and finalised prior to the data cut off for the primary analysis and the updated analysis (see Section 8.4 for database lock details).

The number and percentage of patients with at least one important protocol deviation within each deviation category will be presented based on the FAS. In the instances where multiple deviations for a patient, they will contribute to the count of more than one deviation category.

All protocol deviations will be listed.

12.5 Efficacy Analyses

The data cut-off for the primary analysis will occur approximately 15 weeks after completion of enrolment, when all patients are expected to have had at least 5 cycles of pembrolizumab, at least two post-treatment scans, and the opportunity for a post-treatment tumour biopsy. This analysis will include the primary endpoint of best percentage change in tumour size and all secondary endpoints (excluding Cox proportional hazards for PFS) will be analysed. Investigators and patients will continue to be blinded to randomised study treatment after initial unblinding of data for the primary analysis until the final database lock.

An updated analysis may be performed after approximately 38 progression events have been reported. This updated analysis will include only the secondary endpoints of PFS, and OS in addition to an updated waterfall plot for the primary endpoint of best percentage change in tumour size.

During ongoing review of the overall progression event count, if the predicted timing of the initial and updated analyses are expected to be close in proximity, one analysis may be performed.

Efficacy analyses will be conducted using the FAS. To understand the robustness of the results from important protocol deviations, the primary efficacy analyses will also be performed using the PPS.

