8.4.3 Secondary Endpoints

The secondary endpoints are listed in Section 2.2.

An initial data cut-off will occur approximately 9 weeks after completion of enrolment, when all patients are expected to have had at least 3 cycles of pembrolizumab, at least one post-treatment scan, and the opportunity for a post-treatment tumour biopsy. At this point, the secondary endpoints (with the exception of PFS and OS) will be analysed. An updated analysis may be performed after 38 progression events have been reported. At the updated analysis, ORR, PFS, DoR, DCR, and OS will be summarised and safety data summaries will be updated as appropriate.

The key secondary endpoint of PFS will be summarised by Kaplan-Meier plots presented by treatment groups. Median PFS and the proportion of patients who are progression-free at 3, 6, and 12 months will be summarised along with 80% confidence intervals presented for each treatment group. Patients who have not progressed by the time of the data cut-off for the updated analysis will be censored. The comparison between the treatment groups of PFS will be performed by fitting a Cox proportional hazard model (Cox 1975) with treatment group as the only covariate. The hazard ratio for PFS, based on the profile partial likelihood from the fitted using Cox proportional hazards model, will be calculated as a measure of the treatment effect along with the respective 95% Wald confidence interval and the asymptotic p-value from the Wald test for the difference in the log hazards in the fitted model.

The secondary endpoint of OS will not be formally compared between the treatment groups but will be summarised in a Kaplan-Meier plot together with descriptive statistics, as described for PFS.

The secondary endpoints of ORR, DoR, and DCR will be summarised using descriptive statistics for each treatment group and associated 90% Agresti-Coull confidence interval.

For the key secondary endpoints of numbers of CAFs, CD8⁺ TILs, and regulatory T-cells, and the secondary endpoint of PD-L1 expression analysis in tumour tissue, it is hypothesised based on the mode of action of setanaxib that there will be a reduction in CAFs level and an increase in the number of CD8⁺ TILs. Data will be summarised

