6.0 Introduction

This SAP should be read in conjunction with the study protocol and electronic case report form (eCRF). This version of the SAP has been developed by ICON using protocol version v5.0 dated 12 December 2023 along with the local amendment for the United Kingdom (v4.2 dated 25 April 2023) and CRF v5.0 dated 19 September 2023. Any further changes to the protocol or eCRF that have an impact on the design or the planned statistical analysis will require updates to the SAP.

The initial version of the SAP will be signed prior to the biomarker interim analysis (see Section 11.0 for details). The final version of the SAP, will be issued for sponsor approval prior to the data cut off for the updated analysis (see Section 8.4 for details on the timing of database lock).

A separate Independent Data Monitoring Committee (IDMC) SAP (v1.0 dated 16 December 2022) documents the details of the regular safety and tolerability reviews performed by an unblinded IDMC.

The full set of tables, listings and figures (TLFs) described in this SAP will be produced for the primary analysis and the updated analysis. If there are patients continuing in the study after the updated analysis, a small set of adverse events (AEs), serious adverse events (SAEs) and other selected safety data listings will be updated and included in an addendum to the CSR. The full set of outputs will not be reproduced.

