12.6 Safety Analyses

Safety analyses will be conducted using the Safety Analysis Set and will be summarised descriptively, unless otherwise noted in the sections that follow. All safety related outputs will be produced at the time of both the primary analysis and the updated analysis (see Section 12.5).

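### SAP 12.5 leaves ORR and DoR out of the updated analysis, against SAP 6.0 and the supplied protocol, so both would stay at the primary cut-off

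*SAP*

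**What the plan says.** Four places describe what is produced at the updated analysis.

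- SAP 12.5, Efficacy Analyses: "This updated analysis will include only the secondary endpoints of PFS, and OS", together with a refreshed waterfall plot for the primary endpoint. For the earlier, primary analysis the same section says that "all secondary endpoints (excluding Cox proportional hazards for PFS) will be analysed".
- SAP 6.0, Introduction: "The full set of tables, listings and figures (TLFs) described in this SAP will be produced for the primary analysis and the updated analysis".
- Protocol v4.0, 8.4.3: "At the updated analysis, ORR, PFS, DoR, DCR, and OS will be summarised and safety data summaries will be updated as appropriate".
- SAP 12.6, Safety Analyses: "All safety related outputs will be produced at the time of both the primary analysis and the updated analysis".

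SAP 8.4 points to Section 12.5 for the full account of both analyses. Under SAP 12.5 the update is optional, and it may be merged with the primary analysis if the two would fall close together. SAP 6.1 lists the departures from the protocol. They include the move of the primary cut-off from 9 to 15 weeks and the switch of DoR to Kaplan-Meier, but not the removal of ORR, DoR and DCR from the update.

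**The concern.** A restriction to named endpoints and a promise of the complete output set cannot both be followed. The supplied protocol gives a third list. The programming team therefore has no single specification for the second data cut.

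What is at stake is chiefly the maturity of the response data. DoR needs follow-up after the response, and ORR can still rise as late-enrolled patients have further scans. If 12.5 is followed, the report would show PFS, OS and tumour shrinkage at the later cut beside response rate and duration from the earlier one. The timing also matters. The project team is unblinded at the primary analysis (SAP 8.3 and 12.0), so any ambiguity still open then would be settled by people who have seen results.

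**Working it through.** **1. The plan's own figures.** The update is triggered at about 38 events (SAP 8.1: hazard ratio 0.5, 2-sided 0.20, power above 80%). Schoenfeld's formula gives 4 × (1.2816 + 0.8416)² / (ln 0.5)² = 4 × 4.508 / 0.4805 = 37.5, so 38 events, with power 80.4%. The primary comparison (25 per arm, difference 20, SD 30, 2-sided 0.20) gives 20 / (30 × √(2/25)) = 2.357, and Φ(2.357 − 1.282) = 85.9%, or 85.4% with the noncentral t, against the stated 85%. Both figures reproduce, and neither depends on the point made here.

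**2. The texts side by side, for a separate updated analysis.**

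| Output | SAP 12.5 | SAP 6.0 | Protocol v4.0, 8.4.3 |
|---|---|---|---|
| PFS, OS | yes | yes | yes |
| ORR, DoR, DCR | no | yes | yes |
| Tumour size | waterfall plot only | all outputs | not listed |
| Safety | yes, through 12.6 | yes | yes |

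**3. Which SAP text governs.** SAP 8.4 refers to 12.5 for both analyses, and 12.5 is the specific section. SAP 6.0 cannot be literally right even for the primary analysis, because 12.5 leaves the PFS Cox model out of that analysis. I therefore take 12.5 as governing.

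**4. Follow-up for response at the primary cut-off.** The cut-off is about 15 weeks after the last patient is enrolled (SAP 12.5), and scans fall at Weeks 9 and 15 (SAP 10.9.1). For the last patient enrolled:

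- response at Week 9: 15 − 9 = about 6 weeks of DoR follow-up;
- response at Week 15: 15 − 15 = about none;
- first response after Week 15: not counted in ORR.

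A patient enrolled *x* weeks before the last one has *x* weeks more. The enrolment pattern is not given, so the average follow-up cannot be computed.

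**5. Whether DoR is tabulated at all.** SAP 12.5.4.2 presents DoR only if an arm has at least 5 responders. The protocol cites background response rates of about 15% (Section 1.2) and about 20% (Section 1.3). I assume that the same rate applies in both arms and is reached by the cut-off.

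- 25 per arm: 25 × 0.15 = 3.75 to 25 × 0.20 = 5 responders are expected per arm. P(at least 5 in one arm) is 0.318 to 0.579. P(either arm) is 1 − (1 − 0.318)² = 0.535 to 1 − (1 − 0.579)² = 0.823.
- 35 per arm (the maximum of 70 patients): 0.619 to 0.857 for one arm, and about 0.86 to 0.98 for either.

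Best response can only stay the same or improve as scans accrue, so a re-run at the update cannot lower the number of responders, and may raise it.

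**6. DCR.** Stable disease counts from the first scheduled scan at Week 9 (SAP 10.9.2). A patient with an evaluable scan there is already classified for disease control, and two scans are expected by the cut-off. DCR should hardly move.

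**The case against.** The other side has several good points.

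- **Only one SAP text really governs.** This stands. The sentence in 6.0 is introductory and serves to contrast the two main analyses with a small safety addendum. It still needs correcting, because as written it is wrong.
- **A reader might infer from 6.0 that the primary ANCOVA is tested at 20% at both cut-offs, inflating type I error.** The documents do not support this. SAP 12.5 allows only a waterfall plot for the primary endpoint at the update, SAP 12.5.1 ties the hypothesis to the primary analysis, and the protocol's list for the update omits the primary endpoint. Inflation would require 6.0 to override 12.5 and the later p-value to count. Its size would then depend on a correlation that no document gives: about 22% at 0.99, 24% at 0.95 and 29% at 0.80. I do not put it forward as a consequence of the plan.
- **The missing entry in SAP 6.1 may not be an omission.** This stands as a limit. The SAP cites protocol v5.0 and only v4.0 was supplied, so a later amendment may have changed the list. The conflict between SAP 6.0 and 12.5 does not depend on it.
- **DoR is descriptive, and 6 weeks is the worst case.** Both are true. DoR is censored and summarised by Kaplan-Meier without a formal comparison, so no decision rule rests on it.
- **The waterfall plot need not match ORR at any cut-off.** True: the plot uses target lesions only, whereas response also uses non-target and new lesions. The remaining point is narrower: the two would come from different data cuts.

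**Conclusion.** The point holds in a limited form. Under SAP 12.5, ORR and DoR are reported once, about 15 weeks after enrolment closes, although the supplied protocol has them summarised again at the 38-event analysis. The effect is largest for DoR, with about 6 weeks of follow-up for a last-enrolled Week 9 responder and, at 25 per arm, a 53% to 82% chance that DoR is tabulated at all under the response rates assumed. ORR is affected through late responders, to an extent that the documents do not allow to be computed. DCR is nearly settled.

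This rests on two conditions: that 12.5 governs, and that a separate updated analysis takes place. If the update is merged with the primary analysis or not performed, there is no split between data cuts. A reader might also infer that safety is dropped at the update; SAP 12.6 shows that it is not. Sample size, power and the event target are untouched.

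**What to change.** 1. In SAP 12.5, add ORR, DoR and DCR to the updated analysis. If they are to stay out on purpose, give the reason and, if the current protocol still lists them, record the removal in SAP 6.1.
2. In SAP 6.0, replace the promise of the complete output set at both analyses with a reference to 12.5.
3. Add one sentence to 12.5 or 12.5.1: the primary hypothesis is tested once, at the primary cut-off, and any later tumour-size output is descriptive.
4. Check the revised list against Section 8.4.3 of protocol v5.0.

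No change is needed for safety. The cost is SAP wording and re-running existing programs on the later data cut, with no new data collection. The wording should be settled before the primary analysis is unblinded.
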